9.3.3 Adverse events exemption

Not applicable.

9.3.4 Reporting Procedure to IRB/IEC and to Regulatory Authorities

In addition to reporting the SAE to the Sponsor and Cromsource, the Investigator must also comply with the requirements related to the reporting of SAEs to the IRB which approved the study. The requirements of IRBs vary from one IRB to another; however, as a minimum requirement, the Investigators must promptly report all suspected unexpected serious adverse reaction (SUSAR) to their IRB.

In line with the Sponsor’s procedure and defined timelines, Dompé and Cromsource shall perform an assessment of the expectedness and the causality of each SAE report received and assess regulatory reportability.

Expectedness will be assessed with respect to the current IB [Reference: 4]: due to the early phase of development, all SAEs will be considered unexpected.

For a SAE reported by the Investigator as not related that is subsequently revised to be related by the Dompé, the Investigator will receive a notification.

Events considered “Possible,” “Probable,” and “Highly Probable” related to the IMP treatment will be reported to appropriate regulatory authorities.

In line with provisions set forth in 21CFR312, Dompé Drug Safety shall notify all participating Investigators in an IND safety report of any suspected adverse reaction that is both serious and unexpected and of potential serious risks, from any clinical trials or any other source, as soon as possible, but in no case later than:

- (a) seven calendar days after becoming aware of the information if the event is fatal or life threatening;
- (b) fifteen calendar days after becoming aware of the information if the event is neither fatal nor life threatening.

The investigator in turn shall notify the relevant IRB.

If the results of an investigation show that an adverse drug reaction not initially determined to be reportable is reclassified as reportable, Dompé Drug Safety shall report such reaction in a written safety report as soon as possible, but in no event later than 7/15 calendar days after the determination is made.

Copies of all correspondence relating to reporting of any SUSAR to the IEC/IRB should be maintained in the Investigator’s Files.

Dompé shall also notify FDA in an IND safety report of potential serious risks, from clinical trials or any other source, as soon as possible after Dompé determines the information qualifies for reporting, in particular shall notify of:

- Any suspected adverse reaction that is both serious and unexpected. Dompé must report an adverse event as a suspected adverse reaction only if there is evidence to suggest a causal relationship between the drug and the adverse event.
- Findings from other studies that suggest a significant risk in humans exposed to the drug. Such a finding would result in a safety-related change in the overall conduct of the clinical investigation.
- Findings from animal or in vitro testing that suggest a significant risk in humans exposed to the drug
- Increased rate of occurrence of serious suspected adverse reactions.

Treatment will be unblinded by Dompé Drug Safety prior to submission of a SUSAR to Regulatory Authorities and only cases referred to active treatment will be expeditable for regulatory reporting, in line with law requirements.

Periodic Reporting to Regulatory Authorities

Dompé Drug Safety shall be responsible to prepare and submit appropriate periodic safety updates (Development Safety Update Report – DSUR) to relevant Regulatory Authorities and IRB, if specifically requested.

9.4 Unmasking Of The Study Treatment

Masked information on the identity of the assigned investigational product will be provided for each subject. If the treatment code needs to be broken in the interest of the subject safety, then Dompé Drug Safety must be informed in all cases in which the code was broken and of the circumstances involved.

Additionally, Dompé Drug Safety may be needed to unmask the subject’s treatment if a reported SAE meets criteria of a Suspected Unexpected Serious Adverse Reaction (SUSAR) in order to fulfill expedited regulatory reporting requirements. Unmasked information shall not be disclosed to Investigators.

The identity of the treatments will remain unknown to the subject, Investigator, site staff, and Dompé's clinical research personnel and Cromsource staff (apart from pharmacovigilance).

9.5 Follow-Up Of Subjects With Adverse Events (Aes)

The Investigator is responsible for adequate and safe medical care of subjects during the trial and for ensuring that appropriate medical care and relevant follow-up procedures are maintained after the trial. All AEs should be followed-up to determine outcome of the reaction or until 10 days after the final visit. The Investigator should follow-up the event until resolution or stabilization of the condition. It is the Investigator's responsibility to assure that the subjects experiencing AEs receive definite treatment for any AE, if required.

9.6 Exposure To Investigational Product During Pregnancy

Women of childbearing potential are not excluded from the study as long as adequate birth control methods are being utilized. Women of childbearing potential are defined as all women physiologically capable of becoming pregnant. Adequate birth control methods are summarized in the protocol's exclusion criteria.

Prior to enrollment in the clinical trial, female subjects of childbearing potential and their partners must be advised of the importance of avoiding pregnancy during the entire course of the study treatment and for the 30 days after the study treatment period ends and of the potential risks associated with an unintentional pregnancy. During the trial (during the study treatment period and during the follow up), female subjects are to be instructed to contact the Investigator immediately if they suspect they might be pregnant; in the same way, male subjects who become aware that the partner might be pregnant, are to be instructed to contact the Investigator immediately.

The Investigator must report every pregnancy on a pregnancy report form as soon as possible (within 24 hours from awareness of the pregnancy) to Cromsource/Dompé Drug Safety contacts reported at § 9.3.1, even if no AE has occurred, and follow it to term.

The pregnancy form will be utilized to capture all pregnancy-related information until the birth of the child for both the subject and the partner.

If the pregnancy is associated with an SAE (eg, if the mother is hospitalized for dehydration), in addition to the pregnancy report form, a separate SAE report form must be filed as described in § 11.7 with the appropriate serious criterion (eg, hospitalization) indicated on the SAE report form. Miscarriage, stillbirth and any malformation/disease must be reported as a SAE. Any pregnancy leads to the immediate cessation of the study treatment.

9.7 Adverse Events Causing Treatment Discontinuation

If a subject is withdrawn from the study as a consequence of an AE, this must be recorded and reasoned in the eCRF, and the subject must be followed up until the resolution of the AE or as instructed by the medical monitor.

9.8 Overdose

Cases of overdose (accidental or intentional) shall be reported within 24 hours from the Investigator's knowledge of its occurrence to Dompé Drug Safety and Cromsource, even if not associated with adverse events. This includes reports related to drug intake through different routes (e.g. ingestion), or drug intake with suicidal intentions and consequent drug overdose.

Since in the preclinical toxicology studies in animals and in the multiple ascending dose study performed in healthy volunteers none of the dose has caused an overdose as documented by adverse reaction, for the

purpose of this study, the administration of more than 3 times the total daily dose on any given treatment day should be considered as overdose. Dompé Medical Expert or Cromosome Medical Monitor shall be contacted in case of medical concern.

9.9 Termination Or Halting Of The Study

In the event of two SAE, in separate subjects, with highly probable drug causality the study will be halted with immediate cessation of dosing.

In the event of the study being halted an expert Safety Committee will be created comprising a group of experts and will include the Principal Investigator, an independent specialist Ophthalmologist and an unmasked Statistician.

An operating procedure describing how the Safety Committee works and how it communicates with other study participants will be prepared.

The Committee will review blinded study information (quarterly at a minimum), which will include:

- List of any protocol violations
- Numbers of patient withdrawals/reason for withdrawal.
- Adverse/Serious Adverse Events
- Laboratory Data

The Safety Committee will also be able to request unblinding of patients. The operating procedure will document the planned flow of information in order to describe how the integrity of the study with respect to preventing dissemination of unblinded study information is assured.

Following review of the safety data, the Safety Committee will prepare a written report which will be forwarded to Dompé advising of any recommendations regarding modifications, continuation or termination of the study.

Where changes in the study conduct are recommended to Dompé, sufficient (blinded) information will be provided to allow Dompé to decide whether and how to implement these recommendations.

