NOTE: The term disability means a substantial disruption of a person's ability to conduct normal life functions. This definition is not intended to include experiences of relatively minor medical significance such as uncomplicated headache, nausea, vomiting, diarrhea, influenza, or accidental trauma (e.g., sprained ankle) which may interfere or prevent everyday life functions but do not constitute a substantial disruption).

- results in a congenital anomaly/birth defect;
- is an important medical event

NOTE: An important medical event is an event that may not result in death, be life-threatening, or require hospitalization but may be considered a SAE when, based upon appropriate medical judgment, it may jeopardize the subject's well being and may require medical or surgical intervention to prevent one of the outcomes listed in the definitions for SAEs. Examples of such medical events include allergic bronchospasm requiring intensive treatment in an emergency room or at home, blood dyscrasias or

convulsions that do not result in subject hospitalization or the development of drug dependency or drug abuse.

Death shall always be reported as SAE: a death due to progression of disease would not have a causal relationship to the product. The investigator should report the event immediately to the sponsor, but the sponsor will not report the event as expedited to the regulatory authority. Cause of death shall always be specified when known or duly investigated.

Sight Threatening Event

For this study medically important events comprise the following sight threatening events, which are considered to be of special interest and by default are to be reported as SAEs:

- Adverse Events that caused a decrease in visual acuity of >30 ETDRS letters or > +0.6 LogMAR (compared with the last assessment of visual acuity at the last visit) lasting >1 hour
- Adverse Events that cause a decrease in visual acuity to the level of Light Perception or worse lasting >1 hour
- Adverse Events that require surgical intervention (e.g., conventional surgery, vitreous tap or biopsy with intravitreal injection of anti-infectives, or laser or retinal cryopexy with gas) to prevent permanent loss of sight
- Adverse Events associated with severe intraocular inflammation (i.e., 4+ anterior chamber cell/flare or 4+ vitritis)
- Adverse Events that, in the opinion of the investigator, may require medical intervention to prevent permanent loss of sight.

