Any serious adverse event or sight-threatening event occurring in a subject from the time of study medication administration through the last follow up visit must be reported to the Sponsor within 24 hours, even if the SAE or sight-threatening event does not appear to be drug-related. In the event of an SAE or sight-threatening event, the following steps should be taken;

1. report the SAE or sight-threatening event to Dompé pharmacovigilance contact by fax or e-mail using the SAE form.
2. report the SAE or sight-threatening event to the relevant IRB according to local specific requirements.

Adverse Drug Reaction

An **Adverse Drug Reaction (ADR)** is defined as an adverse event for which there is a reasonable possibility that the drug caused the adverse event. For the purposes of IND safety reporting, "reasonable possibility" means there is evidence to suggest a causal relationship between the drug and the adverse event. Adverse events are to be considered unsuspected if the relationship to the study drug as described in the table in § 9.2.1 is none or unlikely; whereas any AE reported in the study having a possible, probable or highly probable relationship to study drug will be considered as an ADR.

Unexpected Adverse Event Or Unexpected Suspected Adverse Reaction

An adverse event or suspected adverse reaction is considered **unexpected** if it is not listed in the investigator brochure or is not listed at the specificity or severity that has been observed. For example, under this definition, hepatic necrosis would be unexpected (by virtue of greater severity) if the investigator brochure referred only to elevated hepatic enzymes or hepatitis. "Unexpected," as used in this definition, also refers to adverse events or suspected adverse reactions that are mentioned in the investigator brochure as occurring with a class of drugs or as anticipated from the pharmacological properties of the drug, but are not specifically mentioned as occurring with the particular drug under investigation. (CFR-Code of Federal Regulations Title 21 Sec. 312.32). The determination of expectedness should be made on the basis of the current IB [Reference: 4].

Suspected Unexpected Serious Adverse Reaction

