9.2.1 Relationship of Adverse Events to the Investigational Product

The Investigator will assess the relationship between the AE and the investigational medication, according to the criteria in Table 3 below:

Table 3: Relationship of the Adverse Event to the IMP

None (Intercurrent Event)	An event that is not and cannot be related to the Investigational Product, e.g. subject is a passenger in a road traffic accident or surgical intervention performed during the study, but planned before subject enrollment into the study
Unlikely (remote)	Relationship is not likely e.g. a clinical event including laboratory test abnormality with temporal relationship to drug administration which makes a causal relationship improbable and in which other drugs, chemicals or underlying disease provide more plausible explanations
Possible	Relationship may exist, but could have been produced by the subject's condition or treatment or other cause
Probable	Relationship is likely, the AE abates upon discontinuation of Investigational Product and cannot be due to the subject's condition
Highly Probable	Strong relationship, the event abates upon discontinuation of Investigational Product and, if applicable, re-appears upon repeat exposure

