13.5 Discontinuation Of The Study

Dompé farmaceutici s.p.a. reserves the right to terminate the study in its entirety or at a specific study center at any time on the basis of new information regarding safety or efficacy, or if study progress is unsatisfactory, or for other valid administrative reasons.

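### Read literally, the only mandatory halting rule cannot count a death or an SAE that does not improve, because Table 3 makes abatement part of Highly Probable

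*Protocol*

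**What the plan says.** Protocol 9.9 sets the halting rule: "In the event of two SAE, in separate subjects, with highly probable drug causality the study will be halted with immediate cessation of dosing". A Safety Committee is created only once the study has been halted.

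Protocol 9.2.1 sets the causality scale: "The Investigator will assess the relationship between the AE and the investigational medication, according to the criteria in Table 3 below". Table 3 has five grades: None, Unlikely, Possible, Probable and Highly Probable. The top three read:

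- Highly Probable: "Strong relationship, the event abates upon discontinuation of Investigational Product and, if applicable, re-appears upon repeat exposure".
- Probable: "Relationship is likely, the AE abates upon discontinuation of Investigational Product", and in addition the subject's condition must be ruled out as the cause.
- Possible: "Relationship may exist, but could have been produced by the subject's condition or treatment or other cause".

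Protocol 9.1 brings fatal and lasting outcomes within the SAE definition. On death it says "Death shall always be reported as SAE". Persistent disability is also an SAE criterion, and a list of sight-threatening events is reported as SAEs by default.

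Two provisions work alongside the halting rule. Under 9.1, any SAE or sight-threatening event "must be reported to the Sponsor within 24 hours, even if the SAE or sight-threatening event does not appear to be drug-related". Under 13.5, the sponsor may terminate the study "at any time on the basis of new information regarding safety or efficacy".

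**The concern.** A halting rule in healthy volunteers should respond at least as readily to a drug-caused death or irreversible injury as to a serious event that clears up. Here the definitions work the other way. The rule counts only the top causality grade, and that grade requires the event to abate once the drug is stopped. A death cannot abate, and permanent visual loss without recovery does not.

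An investigator who is convinced that the drug caused such an event, and who applies Table 3 as written, cannot give it the grade that 9.9 counts. The automatic halt would not fire, and neither would the formation of the Safety Committee, which depends on that halt. Any stop would then rest on sponsor discretion.

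**Working it through.** The documents give no operating characteristics for the halting rule, so there is no figure to reproduce. The check is a reading of 9.9 against Table 3, followed by a search for any other mandatory stop.

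**Step 1: which grades require abatement.**

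| Table 3 grade | Abatement required? | Counted by 9.9? |
|---|---|---|
| None | No | No |
| Unlikely | No | No |
| Possible | No | No |
| Probable | Yes | No |
| Highly Probable | Yes | Yes |

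In the Highly Probable entry the qualifier follows the conjunction and attaches to re-appearance on repeat exposure. Abatement stands before it, unqualified. The Probable entry has no qualifier.

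**Step 2: grades open to a non-abating event.** 5 grades − 2 that require abatement = 3, the highest being Possible.

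**Step 3: contribution to the halting count.** Grades that 9.9 counts = 1 (Highly Probable). Grades both open to a non-abating event and counted = 0. So k non-abating SAEs among the 20 active subjects give a count of k × 0 = 0 for every k from 0 to 20, against the 2 required. No event rate is assumed.

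**Step 4: other mandatory stops.** None was found.

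- Protocol 13.5 gives the sponsor a right, not an obligation, and ties it to no event count.
- Protocol 11.3 states that there is no Data Monitoring Committee.
- Protocol 9.6 ends study treatment in the event of pregnancy but states no study halt.
- The SAP contains no stopping rule.

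**Step 5: illustration, on assumed inputs.** Let p be the per-subject risk of a drug-caused SAE and f the share of those SAEs that abate and can therefore be graded Highly Probable. Neither is in the documents. With n = 20 active subjects and q = p × f, the probability that the rule fires is

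P(X ≥ 2) = 1 − (1 − q)^20 − 20 q (1 − q)^19.

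For p = 5% and f = 1, q = 0.05 and P = 1 − 0.358 − 0.377 = 0.264 (from unrounded terms). The other cells follow in the same way:

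| Assumed p | f = 1 | f = 0.5 | f = 0 |
|---|---|---|---|
| 5% | 0.264 | 0.088 | 0 |
| 10% | 0.608 | 0.264 | 0 |
| 20% | 0.931 | 0.608 | 0 |

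The last column is the case at issue: if all the drug-caused SAEs are fatal or do not improve, the rule does not fire at any risk. These values of p show how the rule behaves and are not predictions for this product.

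**The case against.** The strongest reply is that the reading is too literal. Section 9.9 does not cite Table 3, whereas the adverse drug reaction definition in 9.1 does cite the table in 9.2.1. Possible is also a poor fit for an event the investigator firmly attributes to the drug, so an investigator forced to choose might take the strong relationship as decisive and grade Highly Probable. Section 9.9 does not say whose judgement counts, and under 9.3.4 the sponsor and CRO also assess causality.

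Safeguards go beyond 24-hour reporting and 13.5. Under 9.3.4, all SAEs are treated as unexpected and Possible is enough for regulatory reporting, with a 7-day limit for fatal or life-threatening cases. The sponsor's safety group unmasks before a SUSAR is submitted. Under 7.6.2, the investigator or a designee supervises dosing in person. No table changes either, because SAP 7.2.8 pools Possible, Probable and Highly Probable as related.

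Much of this stands as a limit on impact. A single such event would be seen quickly by the sponsor and regulators. It does not close the gap. The documents offer no other scale by which 9.9 could be read, and the second causality assessment is not said to use different criteria. An investigator who grades a death Highly Probable is departing from the stated criteria, and a safety rule should not depend on that. Reporting and unmasking make an event visible but do not oblige anyone to stop dosing.

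**Conclusion.** The concern holds as a defect of wording in a participant-safety rule. Applied literally, Table 3 caps a fatal or non-abating SAE at Possible, so such events contribute 0 of the 2 needed to trigger 9.9. This rests on two readings: that the causality term in 9.9 means the Table 3 grade of the same name, and that abatement is a necessary element of that grade. The text supports both.

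The scope is narrow. SAEs that lessen after stopping, including disability or sight-threatening events that improve, can still count. The expected practical impact is low: treatment lasts six days, no SAEs were recorded in the earlier healthy-volunteer study (Protocol 2.6), and the discretionary routes remain open. The correction should still be made, because the omitted outcomes are the gravest ones and the repair costs almost nothing.

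**What to change.** In Table 3, qualify the abatement condition for both Probable and Highly Probable with words such as *where applicable (not required for fatal or irreversible events)*. Alternatively, add one sentence to 9.9 stating that for fatal or irreversible SAEs the causality grade is assigned without the abatement condition.

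Lowering the trigger in 9.9 to Probable would not help, because that grade carries the same condition. The two-event, highly-probable threshold can stay unless the sponsor's medical expert decides otherwise. With it unchanged, a single drug-caused death would still not force a halt.

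The cost is a wording amendment. No analysis changes, and the only downside is a marginally more sensitive automatic halt.

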10 STATISTICS

10.1 Study endpoints

Primary safety endpoints are:

- Incidence of treatment emergent adverse events (TEAEs).
TEAEs are defined as an adverse event (AE), which start after first dose of study treatment. These comprise AEs during the treatment and follow-up period.
- Incidence of treatment emergent adverse events during 1st dose schedule (TEAEs Dose 1).
TEAEs Dose 1 are defined as TEAEs, which start after first dose of study treatment and before administration of the first dose at Treatment Day 2.
- Incidence of treatment emergent adverse events during 2nd dose schedule (TEAEs Dose 2).
TEAEs Dose 2 are defined as TEAEs, which start on/after the first dose at Treatment Day 2 and before Follow Up Day 7 (FU1) visit.

Secondary safety endpoints are:

- Incidence of Follow-Up AEs (FUAE)
FUAEs are defined as TEAEs which start on or after Follow Up Day 7 (FU1) visit visit.
- Incidence of ocular TEAEs by eyes.
- Course of ECG parameters ventricular rate, PR interval, QRS duration and QT interval over all visits.
- Course of vital signs parameters systolic and diastolic blood pressure, pulse rate, respiratory rate and body temperature over all visits.
- Changes from baseline in biochemistry parameters over all visits.
Baseline is defined as the Laboratory assessment of Baseline (D-1) Visit
- Changes from baseline in hematology parameters over all visits.
Baseline is defined as the Laboratory assessment of Baseline (D-1) Visit
- Shift in overall interpretation of urinalysis over all visits. Laboratory assessment at Baseline (D-1) Visit is considered as reference for assessing the shift.
- Course of intraocular pressure by eye over all visits.
- Course of visual acuity score by eyes over all visits
The visual acuity score will be derived as the total numbers of letters, which were read correctly at 4 meter plus the total number of letters read at 1 meter as collected on the eCRF page. When 20 or more letters are read at 4 meters the visual acuity score for that eye is recorded as the number of letters correct at 4 meters plus 30. The subject gets credit for the 30 letters at 1 meter even though they did not have to read them. If no letters are read correctly at either 4.0 meters or 1 meter, then the visual acuity score is recorded as "0."
- Course of LogMAR by eyes over all visits.
The logMAR will be derived as – log (Snellen Equivalent result)
- Course of TFBUT by eye over all visits.

- Course of overall NEI score by eye over all visits.

Primary tolerability endpoints are:

- Change from baseline in VAS ocular tolerability scores at Treatment Day 2 pre-dose in study eye (Tolerability of 1x0.70 µg rh-NGF per day).
Baseline is defined as the pre-treatment assessment at the Baseline (D-1) visit.
- Change from baseline in VAS ocular tolerability scores at D2 8h, D3 pre-dose, D6 pre-dose, D6 8h, D7 (Follow-up Day 7), D8 (Follow-up Day 8), D16 (Follow-up Day 16) in study eye (Tolerability of 6x0.70 µg rh-NGF per day).
Baseline is defined as the pre-treatment assessment at the Treatment Day 2 visit.

Secondary tolerability endpoints are:

- Course of VAS ocular tolerability scores by eye over all visits.
- Intraindividual change in VAS ocular tolerability scores between study eye and fellow (non-study) eye at all study visits.

